#### **12.1.6. Local Skin Reactions**

Investigators and subjects will be required to assess the treated scalp area for local skin reactions (LSRs) at visits 2-11. The following signs and symptoms of contact dermatitis will be assessed:

- Stinging/Burning
- Itching
- Dryness
- Erythema
- Scaling

The Investigator and Subject should report the one integer that best describes the severity of each LSR sign or LSR symptom for the treated scalp area using the scale below.

Local Skin Reactions	
Grade	Descriptor
0	None
1	Mild
2	Moderate
3	Severe

**If a local skin reaction requires treatment or causes an interruption or discontinuation of study medication then the LSR needs to be recorded and assessed as an adverse event.**

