
Study Endpoints:
 
Efficacy:
 
The primary efficacy endpoint is the change from baseline in non-vellus target area hair count (TAHC) using a microphotographic technique.
 
The secondary efficacy endpoints are defined as:
 
 
• development of new hair growth/scalp coverage as assessed by the investigator and the subject using a seven-point rating scale and subject global scalp photographs.
 
• Change from baseline in cumulative target area hair width (TAHW)
 
• Change from baseline in AGA stage according to the Norwood Hamilton scale in males and the Sinclair Scale in females
 
 
Safety:
 
Subjects will be assessed for local skin reactions and adverse events throughout the duration of the trial. In addition, vital signs, ECGs and clinical laboratory assessments will be performed on all subjects at the protocol defined time-points.

Statistical methods:
 
Summary descriptive statistics (N, mean, median, SD) by visit will be provided for all safety and efficacy parameters. The Intent to Treat population will be used for all efficacy assessments and the Safety population will be used for all safety assessments. No data imputation will be used. Primary and secondary efficacy parameters are described below:
 
Primary Efficacy Endpoints:
 
Mean change from baseline in non-vellus target area hair count (TAHC) will be quantified using a microphotographic technique and calculated along with the median, standard deviation, standard error, and 95% confidence limits around each mean change to allow tests of the null hypothesis that the population mean changes are zero.
 
Secondary Efficacy Endpoints:
 
Mean change from baseline in cumulative target area hair width (TAHW) will be quantified using a microphotographic technique and calculated along with the median, standard deviation, standard error, and 95% confidence limits around each mean change to allow tests of the null hypothesis that the population mean changes are zero.

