## **7. INVESTIGATIONAL PLAN**

### **7.1. Overall Study Design**

This is an open-label phase 2 study designed to evaluate the safety and efficacy of ATI-50002 Topical Solution, 0.46% in male and female subjects with androgenetic alopecia. Subjects will be required to apply ATI-50002 study medication to their scalp twice a day for a total of 26 weeks. Subjects will have the option to consent to remain on study for an additional 26 weeks after Visit 10 is completed. All subjects will be required to complete a safety follow up visit 4 weeks after their last application of study medication.

A total of 24 subjects (12 males and 12 females) ages 18-50 years of age with a clinical diagnosis of AGA will be enrolled in the study. Male subjects must have a Norwood Hamilton classification of Type III vertex, IV or V and woman must have a Sinclair Grade of 2, 3 or 4.

Subjects will be required to have a small 1.9 cm diameter circle clipped to ~ 1 mm in length on their balding scalp. Subjects must also agree to have a dot tattoo applied in the center of the clipped area during Visit 2.

Subjects will be required to complete the following treatment visits:

Visit 1: Screening (Day -14-0)

Visit 2: Day 1

Visit 3: Day 21

Visit 4: Day 28

Visit 5: Day 56

Visit 6: Day 84

Visit 7: Day 112

Visit 8: Day 140

Visit 9: Day 168

Visit 10: Day 182

Subjects that consent to remain on study for an additional 6 months of treatment will have the following study visits:

Visit 11: Week 30

Visit 12: Week 35

Visit 13: Week 39

Visit 14: Week 44

Visit 15: Week 48

Visit 16: Week 52

All subjects will be required to have a Follow up Safety Visit 4 weeks post last application of study medication.

All protocol defined treatment assessments are outlined in [Table 2](#) .

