**Table 3: Schedule of Assessments – 6-month Extension Study**

							Follow up Safety/Early Termination Visit
	Visit 11	Visit 12	Visit 13	Visit 14	Visit 15	Visit 16	Visit 17
Treatment week	Week 30	Week 35	Week 39	Week 44	Week 48	Week 52	Week 56
Visit Windows	+7 days	+7 days	+7 days	+7 days	+/-7 days	+7 days	+7 days
Physical Exam 							X
Vital Signs 	X	X	X	X	X	X	X
Clinical Chemistry and CBC 			X	X		X	X

Dihydrotestosterone (DHT), Testosterone, Estrogen, DHEA			X			X	X
Urine Pregnancy Test	X		X	X	X	X	X
ECG			X				X
Norwood-Hamilton classification(males); Sinclair Scale (females)Assessment						X	X
Global Scalp Photograph			X 			X 	X
Macro Scalp Photographs 						X 	
Target Area Hair Count (TAHC) and Target Area Hair Width (TAHW) 						X	
Demonstration of study drug application 	X	X	X	X	X	X	
Dispensing of study medication 	X	X	X	X	X	X	
Investigator Assessment of Hair Growth			X			X	X
Subject Self - Assessment of Hair Growth			X			X	X

Local Skin Reaction Assessment	X	X	X	X	X	X	X
Adverse Events 	X						
Concomitant Therapies	X						

 A physical exam includes: general appearance, examination of head, eyes, ears, nose and throat, respiratory, cardiovascular, abdominal, neurological, musculoskeletal, lymphatic and skin assessment.

 Vital signs include: oral or ear temperature, blood pressure, heart rate, respiration rate.

 Serum chemistry panel to include: albumin, alk phos, ALT, AST, BUN, bicarbonate, calcium, chloride, creatinine, glucose, lactate dehydrogenase (LDH), phosphorus, potassium, sodium, total bilirubin, total protein, uric acid, total cholesterol, LDL, HDL triglycerides, CPK, and complete blood count including differential.

 Canfield staff will review all global photographs within 2 days of the photographs being submitted. If a re-take is required, Canfield will notify the site and the re-take photographs will need to be performed within 7 days of the visit.

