 Canfield staff will review all macro photographs within 2 days of the photographs being submitted. If a re-take is required, Canfield will notify the site and the re-take photographs will need to be performed within 7 days of the visit.

 Sites will take the macro photographs and transmit these to Canfield in order for the Canfield scientists to perform the Target Area Hair Counts and the Target Area Hair Widths. The TAHC and TAHW will be entered into the Canfield database.

 Sites will be required to review with each subject the proper application of the study medication and remind the subjects that they are only to wash their hair with the same shampoo/conditioner and maintain the same hair style throughout the study.

 Subjects will be dispensed bottles of study medication at each monthly visit. Study medication will be weighed prior to dispensing the medication to the subject and upon return of both used and unused bottles.

 All non-serious AEs will be collected from the time of first study medication application until the final study visit. Serious AEs will be collected from the time of consent through the final study visit.

 A final safety follow up visit will be conducted at week 56 (Visit 17). For those subjects that discontinue the study early, they must return to the clinic 4 weeks following the last study medication application for a final safety visit.

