^a Missing is referring to an event that has missing severity and no other event with severity provided for the same preferred term.

NOTE: If a patient had more than one adverse event within an SOC, the patient was counted in the category of greatest known severity.

If a patient had multiple occurrences of the same adverse event, the patient was counted in the category of greatest known severity.

Table 14.3.1.7 Treatment-Emergent Study Medication Related Adverse Events by Maximum Severity Safety Population

PROGAMMING NOTE: Separate pages for Female. Male and Total.

Protocol: ATI-50002-AGA-201

Table 14.3.1.8 Local Skin Reactions – Highest Grade Any Time Post-Baseline Safety Population

		Highest Severity, n (%)								
	•		Fema	ale			Ma	ale		
Assessor	Sign	Mild	Moderate	Severe	Total	Mild	Moderate	Severe	Total	
Any	Any	xx (xx.x)	xx (xx.x)	xx (xx.x)	xx (xx.x)	xx (xx.x)	xx (xx.x)	xx (xx.x)	xx (xx.x)	
Investigator	Any	xx (xx.x)	xx (xx.x)	xx (xx.x)	xx (xx.x)	xx (xx.x)	xx (xx.x)	xx (xx.x)	xx (xx.x)	
_	Erythema	xx (xx.x)	xx (xx.x)	xx (xx.x)	xx (xx.x)	xx (xx.x)	xx (xx.x)	xx (xx.x)	xx (xx.x)	
	Scaling	xx (xx.x)	xx (xx.x)	xx (xx.x)	xx (xx.x)	xx (xx.x)	xx (xx.x)	xx (xx.x)	xx (xx.x)	
	Dryness	xx (xx.x)	xx (xx.x)	xx (xx.x)	xx (xx.x)	xx (xx.x)	xx (xx.x)	xx (xx.x)	xx (xx.x)	
Subject	Any	xx (xx.x)	xx (xx.x)	xx (xx.x)	xx (xx.x)	xx (xx.x)	xx (xx.x)	xx (xx.x)	xx (xx.x)	
_	Stinging/burning	xx (xx.x)	xx (xx.x)	xx (xx.x)	xx (xx.x)	xx (xx.x)	xx (xx.x)	xx (xx.x)	xx (xx.x)	
	Itching	xx (xx.x)	xx (xx.x)	xx (xx.x)	xx (xx.x)	xx (xx.x)	xx (xx.x)	xx (xx.x)	xx (xx.x)	

^a Percentages are based on the total number of patients safety population for the group.

NOTE: Patients are counted only once foreach sign at the highest severity grade.

Protocol: ATI-50002-AGA-201

Table 14.3.1.8 Local Skin Reactions – Highest Grade Any Time Post-Baseline Safety Population

_			Highest	Severity, n (%)
			Tot	al	
Assessor	Sign	Mild	Moderate	Severe	Total
Any	Any	xx (xx.x)	xx (xx.x)	xx (xx.x)	xx (xx.x)
Investigator	Any	xx (xx.x)	xx(xx.x)	xx (xx.x)	xx (xx.x)
	Erythema	xx (xx.x)	xx (xx.x)	xx (xx.x)	xx (xx.x)
	Scaling	xx (xx.x)	xx (xx.x)	xx (xx.x)	xx (xx.x)
	Dryness	xx (xx.x)	xx (xx.x)	xx (xx.x)	xx (xx.x)
Subject	Any	xx (xx.x)	xx (xx.x)	xx (xx.x)	xx (xx.x)
	Stinging/burning	xx (xx.x)	xx (xx.x)	xx (xx.x)	xx (xx.x)
	Itching	xx (xx.x)	xx (xx.x)	xx (xx.x)	xx (xx.x)

^a Percentages are based on the total number of patients safety population for the group.

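### Section 12.1.6 ends local skin reaction grading at Visit 11 but Table 3 continues it to Visit 17, and the SAP outputs would not show missing extension grades

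*Protocol*

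**What the plan says.** **Visit list in the assessment section.** Protocol Section 12.1.6: "Investigators and subjects will be required to assess the treated scalp area for local skin reactions (LSRs) at visits 2-11". This section also holds the list of signs and symptoms and the 0 to 3 grading scale.

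**Schedules.** Table 2 marks LSR grading at Visits 2 to 10 and at the follow-up/early termination visit. In Table 3 (extension), the row "Local Skin Reaction Assessment" is marked in all seven columns, Visits 11 to 17.

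**Synopsis.** Under Study Endpoints, Safety: "Subjects will be assessed for local skin reactions and adverse events throughout the duration of the trial". The synopsis paragraph on safety assessments also promises LSR results by visit, and Section 13.1 promises by-visit descriptive statistics, including N, for all safety parameters.

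**Timing.** Section 7.1 gives "Visit 11: Week 30" and "Visit 16: Week 52". Table 3 places Visit 17, the off-drug follow-up, at Week 56. The second 26 weeks are optional: "Subjects will have the option to consent to remain on study for an additional 26 weeks after Visit 10 is completed".

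**SAP.** The only LSR table in the list of safety tables is Table 14.3.1.8, "Local Skin Reactions – Highest Grade Any Time Post-Baseline". Its columns are Mild, Moderate, Severe and Total, and its percentages use all safety-population patients in the group. A footnote to Appendix 16.2.3.5 (the LSR listing) gives an assessor's visit the same entry whether all signs were grade 0 or were not done.

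**The concern.** Tolerability is part of the primary objective (Section 6.1), and graded LSRs are the plan's scheduled measure of local tolerability for a topical product. Two operative parts of the protocol give different grading schedules for the same extension subject. I found no rule that ranks the schedule above the text. Section 7.1 does not settle it either, because it refers to Table 2 for the protocol-defined assessments and does not name Table 3.

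If a site works from Section 12.1.6, graded LSR data for its extension subjects end at Week 30. The planned outputs would then give a worst grade labelled as covering any time after baseline, with nothing to show that the later visits were not graded.

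**Working it through.** The plan states no figure on this point, so the check is a count of visits and weeks and a comparison of passages.

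**1. Grading visits for a subject who completes the extension**

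| Source | Visits | Post-baseline visits |
|---|---|---|
| Tables 2 and 3 | 2 to 17 (16 visits) | 3 to 17: 17 − 3 + 1 = 15 |
| Section 12.1.6 | 2 to 11 (10 visits) | 3 to 11: 11 − 3 + 1 = 9 |
| Difference | 12 to 17 | 15 − 9 = 6 |

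6 / 15 = 40%. The six visits fall at Weeks 35, 39, 44, 48, 52 and 56. Five are on treatment and one is the follow-up.

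**2. Treatment time after the last grade under Section 12.1.6**

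The last grade is at Visit 11, Week 30, and treatment ends at Week 52. (52 − 30) / 52 = 22 / 52 = 42%.

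**3. Subjects who do not enter the extension**

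Their final safety visit is at Week 30. If Visit 11 is read as that visit, Section 12.1.6 and Table 2 give the same coverage, so nothing is lost.

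**4. Likely source of the mismatch**

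Three neighbouring sections also treat Visit 11 as the end of the study: 12.1.3 (physical examination), 12.1.4 (ECG) and 12.1.7.1 (chemistry). The amendment history shows that Version 4.0 added the extension and its separate schedule table. This pattern fits visit numbering that was not updated, rather than a decision to stop grading.

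**5. Effect on the worst-grade table**

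For each subject and sign, the highest grade over Visits 3 to 11 can only be equal to or lower than the highest over Visits 3 to 17. Any error therefore goes one way, towards fewer or milder reactions. The documents give no LSR rates, so its size in patients cannot be computed.

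**6. Whether the SAP would show the gap**

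- Table 14.3.1.8 has no column for missing or for no reaction, and its denominator is everyone treated. Ungraded visits therefore count as reaction-free. By contrast, the SAP does give a missing category in the tables for adverse event severity (14.3.1.6) and ECG shift (14.3.3).
- In Appendix 16.2.3.5, a listed visit at which nothing was graded reads the same as a visit with all grades 0.
- A by-visit table with N would show the gap, but the list of safety tables contains none for LSRs.

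**The case against.** The strongest reply is that this is one stale sentence. Table 3 is the only schedule written for the extension and it marks LSR grading at every visit. The synopsis agrees with it. A site would have to disregard Table 3 at visit after visit to stop at Week 30. The protocol also promises a by-visit LSR summary, which would expose ungraded visits. Much of this stands. The intent can be recovered from the documents, and nothing in them shows that any site followed Section 12.1.6 instead. It does not close the point, because Section 12.1.6 is current text, it holds the grading scale that staff must use, and the promised by-visit summary is not in the SAP's list of tables.

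Three stronger readings are tempting, and the documents do not support them.

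- A reader might infer that all tolerability data stop at Week 30. They do not. Adverse events are collected to the final study visit, and under Section 12.1.6 an LSR that needs treatment or leads to a pause or stop of medication must be recorded as one. What could be lost is the scheduled grading of reactions below that threshold.
- A reader might infer that site differences would make LSR rates non-comparable between centres. This is a single-arm study at about 3 centres, Table 14.3.1.8 reports Female, Male and Total only, and no between-site LSR comparison is planned.
- A reader might think that a footnote limiting the denominator to subjects graded after Visit 11 would repair the table. Table 14.3.1.8 has no extension-period percentages for such a denominator to apply to, and the rule would ignore grades taken at Visit 11, which Table 3 counts as an extension visit.

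**Conclusion.** The contradiction is real and should be corrected. It probably comes from an incomplete update of Section 12.1. Its reach is limited to subjects who consent to the optional extension, an unknown part of the 24 planned. For each such subject who attends every visit, following Section 12.1.6 as written would drop 6 of 15 post-baseline grading visits (40%) and leave the last 22 of 52 treatment weeks (42%) without a graded LSR.

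The point is more than editorial because the planned SAP outputs would not reveal the loss, and any resulting error in the worst-grade table could only understate reactions.

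This rests on two assumptions. The first is that some site might follow the text over the schedule, which the documents neither show nor rule out. The second is that the SAP's table list, shells and listings are the full set of planned LSR outputs. The SAP text available for this review consists of those parts only.

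**What to change.** **Protocol.** Reconcile the visit list in Section 12.1.6 with Tables 2 and 3, so that it covers Visits 2 to 10, extension Visits 11 to 16, and the follow-up/early termination visit. Check the Visit 11 references in Sections 12.1.3, 12.1.4 and 12.1.7.1 in the same pass, since they carry the same numbering.

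**SAP.** Add one by-visit LSR table that shows, at each scheduled visit including the extension visits, the number of subjects with a grade and the distribution of grades. This delivers the by-visit summary that the synopsis already promises. In Appendix 16.2.3.5, list not-done as its own entry, separate from grade 0. Table 14.3.1.8 can then stay as it is, read alongside the by-visit counts.

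**Cost.** One protocol sentence, one added table and one listing change. No assessment is added beyond those already in Table 3.

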### 12.1.7. Laboratory Assessments

#### 12.1.7.1. Clinical Chemistry/Hematology

All subjects are required to have a blood chemistry panel performed at Visit 1 (Screening), Visit 5 (Day 56), Visit 7 (Day 112), Visit 9 (Day 168), Visit 10 (Day 182) and Visit 11 (Day 210) /Safety Follow up Visit. A qualified staff member will collect non-fasting blood samples and ship the samples to a central laboratory for analysis. The following tests will be performed:

Chemistry Panel	Complete Blood Count
Albumin	Hematocrit
Alkaline phosphatase	Hemoglobin
Alanine aminotransferase (ALT)	Platelet count
Aspartate aminotransferase (AST)	Red blood cell morphology
Blood urea nitrogen (BUN)	Red blood cell count
Bicarbonate	White blood cell count
CPK	
Calcium	White blood cell differential
Chloride	% & absolute
Creatinine	Basophils
Glucose	Eosinophils
Lactate dehydrogenase (LDH)	Lymphocytes
Phosphorus	Monocytes
Potassium	Neutrophils
Sodium	
Total bilirubin	
Total protein	

Uric Acid  
Total cholesterol, LDL, HDL  
Triglycerides  
Total Iron Binding Capacity (TIBC) (Visit 1 only)  
Serum iron (Visit 1 only)  
Serum Ferritin (Visit 1 only)  
Testosterone  
Estrogen  
DHEA  
Dihydrotestosterone (DHT)  
Serum PSA (males only; Visit 1 only)  
Lutenizing Hormone (LH) (Visit 1 only)  
Thyroid Panel (Visit 1 only) (including TSH, Total T4,  
Total T3, Free T4, Free T3, Reverse T3 (rT3), T3U,  
Free T4 Index, and TPO and AntiTG antibodies)

#### **12.1.7.2. Virus Serology**

All subjects will be required to have a QuantiFERON TB blood test performed at screening to assess for exposure to the tuberculosis virus. At Visit 1 (Screening) a blood sample will be drawn and sent to a central laboratory for analysis. Subjects that test positive will not be eligible for enrollment to the study.

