Target Area Hair Count (TAHC) and Target Area Hair Width (TAHW) 		X			X		X			X	
Demonstration of study drug application 		X		X	X	X	X	X	X	X 	
Dispensing of study medication 		X		X	X	X	X	X	X	X 	

	Screening	Baseline	Treatment								Follow up Safety/Early Termination Visit 
	Visit 1	Visit 2	Visit 3	Visit 4	Visit 5	Visit 6	Visit 7	Visit 8	Visit 9	Visit 10	
			Week 3	Week 4	Week 8	Week 12	Week 16	Week 20	Week 24	Week 26	4 weeks post last application of ATI-50002
Treatment Day	-14 to 0	1	21	28	56	84	112	140	168	182	
Visit Windows	N/A	N/A	+/- 3 days	+/-4 days	+7 days	+/-7 days	+7 days	+/-7 days	+/-7 days	+7 days	+7 days
Investigator Assessment of Hair Growth					X		X			X	
Subject Self - Assessment of Hair Growth					X		X			X	
Local Skin Reaction Assessment		X	X	X	X	X	X	X	X	X	X
Adverse Events 							X				
Concomitant Therapies							X				

A written, signed ICF must be obtained from each subject prior to performing any study related procedure

 A physical exam includes: general appearance, examination of head, eyes, ears, nose and throat, respiratory, cardiovascular, abdominal, neurological, musculoskeletal, lymphatic and skin assessment.

Vital signs include: oral or ear temperature, blood pressure, heart rate, respiration rate (height and weight at baseline only).

 Prior therapies or treatments a subject received to treat his/her AGA must be documented for each subject.

 Serum chemistry panel to include: albumin, alk phos, ALT, AST, BUN, bicarbonate, calcium, chloride, creatinine, glucose, lactate dehydrogenase (LDH), phosphorus, potassium, sodium, total bilirubin, total protein, uric acid, total cholesterol, LDL, HDL triglycerides, CPK, and complete blood count including differential.

 All subjects must have a blood sample drawn to test for the tuberculosis virus. The blood sample will be sent to a central laboratory for analysis and results must be received prior to enrolling the subject.

 The investigational study staff will be required to identify target area of the scalp that is located in an actively balding area. Directions for proper hair clipping are outlined in Section 9.2. Sites will be required to apply a permanent dot tattoo to the subject’s scalp to identify the target hair area.

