### **8.2. Subject Exclusion Criteria**

Subjects are excluded from this study if any 1 or more of the following criteria is met:

1. Females who are nursing, pregnant, or planning to become pregnant for the duration of the study and up to 30 days after the last application of study medication
2. Clinical diagnosis of alopecia areata or other non-AGA forms of alopecia.
3. Scalp hair loss on the treatment area, due to disease, injury or medical therapy.

4. Active skin disease on the scalp (such as psoriasis or seborrheic dermatitis) or a history of skin disease on the scalp that in the opinion of the investigator would interfere with the study assessments of efficacy or safety.
5. Evidence of hypogonadism defined as serum testosterone < 250ng/dl and/or LH>20mU/ml in males.
6. Active unstable thyroid disease, including subjects on therapy for either hyperthyroidism or hypothyroidism unless their dose of thyroid medication has been stable for 3 months prior to V2 and serum TSH is normal.
7. Subjects with non-pigmented hair.
8. Subjects unable to comply with the following required washout periods:
  - Scalp promoting hair growth products (e.g. minoxidil, finasteride, dutasteride, saw palmetto) for 6 months prior to Visit 2.
  - Anti-androgenetic therapies (e.g. spironolactone, ketoconazole, flutamide, cyproterone acetate) for 6 months prior to Visit 2.
  - Hair transplantation or hair weaving within 6 months of Visit 2
  - Anabolic steroids for 6 weeks prior to Visit 2.
  - Oral or topical JAK inhibitors 3 months prior to Visit 2
  - Platelet rich plasma treatment within 6 months of Visit 2
  - Hair Laser, light or energy treatments to the target hair area within 3 months of Visit 2.
  - Systemic steroids for more than 14 consecutive days in the 2 months prior to Visit 2.
  - Chemotherapy or cytotoxic agents within 12 months of Visit 2.
  - No prior radiation to the scalp.
9. History of, current or suspected systemic or cutaneous malignancy and /or lymphoproliferative disease, other than subjects with: a history of adequately treated and well healed and completely cleared non-melanoma skin cancers (basal or squamous cell carcinoma) treated successfully with no evidence of disease.
10. History of human immunodeficiency virus (HIV), hepatitis B or C.
11. Current herpes zoster infection.

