12. Evidence of active, latent or inadequately treated Mycobacterium tuberculosis infection, or history of incompletely treated or untreated tuberculosis. Subjects who have successfully completed therapy for latent tuberculosis may participate.
13. History of serious local infection (e.g., cellulitis, abscess) or systemic infection including but not limited to a history of treated infection (e.g., pneumonia, septicemia) within 3 months prior to Visit 1. Subjects on an antibiotic for a non-serious, acute local infection must complete the course prior to enrollment into the study.
14. Participation in an investigational drug, device, or biologic trial in which administration of an investigational drug, device, or biologic within 30 days or 5 half-lives (whichever is longer) of Visit 2. Subjects who have participated in a study of an investigational drug, device or biologic agent for androgenetic alopecia within 1 year of screening will be eligible to participate only with individual permission from the Medical Monitor.
15. Sensitivity to any of the ingredients in the study medications.
16. Screening ECG findings of:
  - QTcF >450msec for males or >470msec for females (use of the ECG algorithm is acceptable for this purpose)
  - Heart rate < 45 or > 100 beats/minutes (inclusive)

- Rhythm disturbance other than sinus arrhythmia or ectopic supraventricular rhythm (ectopic atrial rhythm)
- Conduction disturbance including PR >240msec, pre-excitation (delta wave and PR <120msec), second degree or higher AV block
- Acute or chronic signs of ischemia
- Left Bundle Branch Block
- Prior myocardial infarction

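### Exclusion 12 and section 12.1.7.2 of the protocol give different answers for one kind of subject: treated for latent tuberculosis and QuantiFERON-positive at screening

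*Protocol*

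**What the plan says.** Three places in the protocol bear on tuberculosis screening.

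- **Exclusion 12 (section 8.2; same wording in the Synopsis).** The excluding part reads "Evidence of active, latent or inadequately treated Mycobacterium tuberculosis infection, or history of incompletely treated or untreated tuberculosis". The sentence after it is a permission: "Subjects who have successfully completed therapy for latent tuberculosis may participate". It does not mention a test result.
- **Section 12.1.7.2, Virus Serology.** Testing is universal: "All subjects will be required to have a QuantiFERON TB blood test performed at screening to assess for exposure to the tuberculosis virus". The consequence is equally general: "Subjects that test positive will not be eligible for enrollment to the study". It does not mention earlier treatment.
- **Table 2, footnote 6.** On timing, the footnote says that "results must be received prior to enrolling the subject". It does not say what to do with a positive result.

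In the SAP, Appendix 16.2.1.9 is a mock-up listing that appears to record, by number, the inclusion and exclusion criteria a patient failed. Appendix 16.2.1.10 lists protocol violations. Neither mentions tuberculosis testing.

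**The concern.** A treated subject is not exempt from the test, and the result must be in hand before enrolment. A site will therefore meet the question directly if such a subject tests positive. Exclusion 12 lets the subject in and section 12.1.7.2 keeps the subject out.

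Two things are at stake. The first is consistency of enrolment across the roughly three centers, on a criterion that screens for infection risk before exposure to a JAK1/3 inhibitor. Section 8.3 treats severe infection as a reason for permanent discontinuation. The second is classification. Section 15.4 requires every protocol violation to be reported to the IRB. Its definition covers departures from the eligibility criteria or from study procedures that may raise risk to the subject. Section 12.5 says that a mere deviation does not involve the eligibility criteria. The status of such an enrolment should not depend on which section the site or the monitor happened to consult.

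**Working it through.** No arithmetic applies. The check is to cross-classify subjects by treatment history and test result, then read each rule literally.

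| Profile at screening | Exclusion 12 | Section 12.1.7.2 | Agree? |
|---|---|---|---|
| Latent TB therapy completed, test positive | Allowed by its last sentence | Not eligible | **No** |
| Latent TB therapy completed, test negative | Allowed by its last sentence | Not barred | Yes |
| No completed therapy, test positive | Excluded, if the result is read as evidence of infection | Not eligible | Yes, on that reading |
| No TB history, test negative | Not excluded | Not barred | Yes |

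The disagreement is confined to the first row.

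Next, does anything else in the documents settle that row?

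1. Table 2 footnote 6 fixes when the result must be available, not what follows from it.
2. Section 8.2 opens with "Subjects are excluded from this study if any 1 or more of the following criteria is met". This makes the numbered criteria cumulative with one another, but 12.1.7.2 is not one of them.
3. Neither exclusion 12 nor 12.1.7.2 cites the other, and no order of precedence between sections is given.

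Finally, follow an enrolled first-row subject through the SAP listings.

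1. Appendix 16.2.1.9 works from numbered criteria. Under the last sentence of exclusion 12 the subject has failed none of them on tuberculosis grounds, so need not appear.
2. The same enrolment departs from the literal text of 12.1.7.2, so it would belong in Appendix 16.2.1.10.

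The subject could therefore be recorded as eligible in one listing and as a violation in the other, with no rule in the plan to reconcile the two.

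**The case against.** The strongest reply is that the two rules can be obeyed together. The last sentence of exclusion 12 is a permission that qualifies that exclusion; it does not oblige a site to enrol anyone. Section 12.1.7.2 can then be read as a further condition: a treated history is acceptable, but the test must be negative. A site that turns away every positive subject breaches neither passage, and the permission still has work to do for treated subjects who test negative.

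Much of this stands. The reading is coherent, so the conflict is not a logical impossibility. But the protocol does not state it. It adds to exclusion 12 a test condition that is not written there. The opposite reading adds to 12.1.7.2 an exception that is not written there either. A site has to supply text whichever way it decides.

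Three stronger conclusions might be inferred and are not supported:

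- **That the safety population becomes uncertain.** Section 13.4 summarizes all enrolled and treated subjects, and the percentages in SAP Table 14.1.1.1 rest on patients with at least one application. Tuberculosis eligibility enters neither. The SAP tables available show only ITT and safety populations, and none removes ineligible subjects.
- **That such an enrolment would be fully compliant on one reading.** It always departs from the literal words of 12.1.7.2, whatever exclusion 12 allows.
- **That the number affected can be estimated.** The documents give neither the frequency of treated latent infection among those screened nor how often treated subjects test positive. Any percentage applied to the 24 planned subjects would be a guess.

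**Conclusion.** The inconsistency is real and narrow. For subjects who have completed latent TB treatment and test positive at screening, exclusion 12 and section 12.1.7.2 point in opposite directions, and nothing else in the documents decides between them. For every other profile there is no demonstrated conflict.

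The consequences are possible differences between sites in who is enrolled, and uncertain classification of any such subject between the eligibility and violation listings. The listings as a whole remain interpretable. No endpoint, confidence interval or sample-size figure depends on the point, and the number of subjects affected may well be zero in a study of 24.

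The conclusion rests on the wording alone. The one interpretive step is that Appendix 16.2.1.9 will be filled by criterion number, as its mock-up suggests. The case for acting is that this is a safety eligibility rule and the correction is very small.

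**What to change.** Reconcile the Synopsis (exclusion 12), section 8.2 (exclusion 12) and section 12.1.7.2 into a single rule. Each should refer to the other and say explicitly how a positive QuantiFERON in a subject treated for latent TB is handled. Two forms of wording are available once the sponsor's medical monitor has decided:

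- if the allowance is meant to cover test-positive treated subjects, 12.1.7.2 needs the exception written in;
- if it is not, the last sentence of exclusion 12 needs to be limited to those who test negative.

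This review does not say which is right.

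For the SAP, a note that Appendices 16.2.1.9 and 16.2.1.10 classify such subjects by the reconciled rule is enough; the mock-up formats need not change. If enrolment has already closed, which the documents do not state, the remaining task is to settle the rule for those listings and check whether any enrolled subject fits the profile.

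The cost is about one sentence and a cross-reference in an amendment. No analysis changes.
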